5.3.2 Leveraging the nationwide network for CHR recruitment (aim 1)

The clinical infrastructure described above provides clinical services for young people with a range of clinical presentations. In the 2018-2019 financial year, approximately 3,000 young people accessed HEP services, 1000 young people accessed Orygen Specialist Program, and over 5,000 young people accessed the 5 *headspace* clinics involved in the network (i.e., 6000 across the clinics directly operated by Orygen)¹⁹. Data on CHR status of this pool of patients is available from a range of sources including our cohort studies^{26, 27}, the Staged Treatment in Early Psychosis (STEP) study²⁸, and clinical service records. These data sources indicate that 15% of HEP patients, 15% of Orygen Specialist Program patients, and ~30% of *headspace* patients meet CHR criteria. In raw numbers, this translates to ~2,000 CHR patients/year. Therefore, our recruitment target of 468 CHR patients per year over a two-year period (937 in total) equates to recruiting <25% of the pool of eligible patients. This is highly feasible, given that recruitment rates to current CHR studies being conducted by our group (across the same clinics) consist of 50% of eligible patients.

5.3.3 Extending minimal data sets in order to test and develop prediction models

Both the *headspace* and HEP clinics provide a sampling frame with linked minimal data sets. Our network of *headspace* clinics collect a minimal data set as part of routine clinical practice^{25, 29}. The AEPCC will establish a clinical registry for all early psychosis patients, including CHR patients. While these minimal data sets are invaluable for better characterizing this clinical population and standardizing assessment and routine data collection practice, they are *not sufficient for building and testing prediction models with high levels of accuracy*, which is required in this research field.

The minimal data set of *headspace* patients includes: reason for presentation, Kessler Psychological Distress Scale (K10), stage of illness, diagnosis, and functioning²⁵. The HEP minimal data set includes demographics, referral pathways, prior treatment, stage of psychotic illness (CHR or FEP, determined using the Comprehensive Assessment of At Risk Mental States [CAARMS]), general distress (K10), functioning (Social and Occupational Functioning Assessment Scales [SOFAS]) and quality of life, and details of treatment received, including medication, inpatient admissions, psychosocial treatment, and patient and family satisfaction with treatment.

In the current study, we will work with the Data Processing, Analysis, and Coordination Center (DPACC) to build on these minimal data sets to collect a far more comprehensive data set, supported by a number of conceptual and analytical advances in the field, but also balanced with issues of feasibility and awareness of participant burden. We briefly summarise these conceptual and analytical advances below.

Dynamic prediction, early warning signs and network theory: Over recent years, in collaboration with European colleagues, we have approached modelling and predicting onset and evolution of psychotic disorder and other mental disorders through a dynamic (i.e., time-dependent or time-variable) lens in order to supplement the standard static prediction approach that relies exclusively on baseline (clinic or study entry) data³⁰⁻³⁶. This draws on approaches that have proven to be useful in other areas of psychiatry (e.g., predicting relapse in depression^{37, 38}) and which have yielded greater predictive accuracy in other areas of medicine, such as cardiovascular research³⁹ and oncology⁴⁰, as well as in other disciplines that model complex systems, such as ecology^{41, 42} and economics⁴³. Consistent with our clinical staging model⁴⁴⁻⁴⁶, this dynamic approach to prediction is well-suited for incorporating the highly changeable and mercurial nature of psychopathology, particularly in the early stages of disorder³⁴. Analytical tools to operationalise these dynamic approaches include various forms of time series analysis, joint modelling, and network analysis.

Time series analysis involves analysis of a series of data points indexed in time order. Patterns in the data that emerge over time can be used for the purpose of forecasting future values. This approach has been more widely deployed in other areas of psychiatry, e.g. depression and transdiagnostic prediction^{36, 38, 47, 48}, than in psychosis prediction. In these other areas, particular temporal patterns in the data, including increase in emotional state correlating with itself over time ('temporal autocorrelation') and increased variance and

change in the association between emotions over time have proven valuable as ‘early warning signs’ of an imminent change in mental state (e.g., ‘tipping point’ into a depressive episode)^{38, 48, 49}. In the area of psychosis and psychosis risk, the focus has instead been on the proximal relationship between everyday events/contexts and momentary fluctuations in mental state, such as stress sensitivity assessed using ecological momentary assessment (EMA), rather than on prediction of clinical outcomes⁵⁰⁻⁵³.

Joint modelling is an emerging statistical methodology that uses longitudinal, repeat assessment of variables (‘time-dependent predictors’) to predict outcomes with variable time frames. It is therefore a useful means of *adjusting prognosis* for patients as relevant variables are assessed repeatedly over time, yielding dynamic risk calculation. Our group, led by Associate Investigator [name], has already introduced this approach to CHR prediction research³⁰⁻³³. In this work, a joint model using repeat monthly assessments yielded superior prediction statistics for conversion to psychosis compared to static baseline assessment in the same CHR cohort^{31, 33}. Comparing the receiver operating characteristic (ROC) curves, the area under the curve (AUC) of the joint model was significantly greater than that of the baseline model (p-value=0.019). Also of note is that, for the point closest to the ideal point (0,100), the joint model showed substantially higher sensitivity (83% vs. 69%) and similar specificity as the baseline model (72% vs. 74%), indicating that the joint model was able to detect more converted cases yet with little increase in false positive rate. The strong predictive performance of this approach has recently been confirmed by another group in an independent data set⁵⁴.

Network theory posits that symptoms are not all explained by a shared underlying cause, as in the traditional latent disease model (e.g., lung cancer being the underlying common cause of various symptoms such as shortness of breath, chest pain, and coughing up blood)⁵⁵. Rather, mental disorders are seen as complex dynamic systems in which symptoms and psychological, biological and social components have autonomous causal power to influence and trigger each other^{56, 57}. If symptoms form patterns of mutual reinforcement and feedback loops, the system as a whole may become trapped or ‘locked’ in a state of extended symptom activation, a point at which a mental disorder may be diagnosed (e.g., conversion to psychosis). Network analysis models the pairwise relationship (‘edges’) between symptoms (‘nodes’) cross-sectionally and dynamically over time (using time series), showing interactions between symptoms⁵⁵. It is plausible that this ‘locked’ state is more likely to occur in biologically vulnerable people; however, this process may be interrupted by psychosocial and biological early intervention strategies. These possibilities can be assessed in the current dataset by examining interactions between data modalities over time (e.g., digital momentary assessments and biomarkers), as well as modelling impact of treatment exposure.

Importantly, these approaches are well suited for modelling the natural course of disorder (e.g., increasing symptomatology) and the impact of time-varying exposures (e.g., adverse life events) as well as treatment. They can be applied to any type of data. Although phenotypic data has been the principal type of data used in these analytical approaches to date, they can also be applied to biomarker data. For example, persistent language disturbance⁵⁸, accelerated grey matter loss⁵⁹ or decreases over time in EEG-assessed

mismatch negativity⁶⁰ or N-1 suppression scores⁶¹ would all be appropriate for statistical modelling using these approaches. These dynamic analytical approaches will be applied to the data collected in the current network, in collaboration with the DPACC.

Multimodal prediction: In addition to dynamic prediction approaches, multimodal (using multiple assessment domains or levels of analysis) have also proven valuable in enhancing predictive accuracy. An example of this approach is probabilistic multimodal modelling using the odds ratio form of Bayes' Rule to develop probabilistic models of outcome (e.g., conversion to psychosis) based on data from combining different modalities (e.g., clinical data alone vs clinical data plus neuroimaging data vs clinical data plus neurocognitive plus neuroimaging data)^{62, 63}. Recent empirical work by the research team has indicated that this approach can improve on prediction based on data from one domain alone⁶³. For example, we recently showed that a probabilistic multimodal model combining clinical history, symptoms, and fatty-acid biomarkers identified over 70% of CHR cases who converted to psychosis within one year, compared with 28% identified by standard CHR criteria^{32, 63}. This approach in fact models, and can be used to further refine, real clinical decision-making regarding the need for further types of diagnostic assessments based on outcomes of each step in assessment, accounting for the baseline risk of conversion in the population from which the individual derives (e.g., help-seeking in a specialist clinic vs general population samples). This can directly inform indicated treatment based on level of risk established. Similarly, in the EU-based PRONIA study⁶⁴, supplementing clinical ratings with structural imaging (MRI) was found to increase predictive accuracy for functional outcome in CHR patients from 77% (clinical measures alone) to 83% (clinical measures + MRI). However, adding different data types has not always been found to increase predictive accuracy substantially. For example, Perkins et al⁶⁵ recently found that adding a polygenic risk score (PRS) to a risk calculator based on patient history, clinical variables and neurocognitive variables only modestly improved psychosis risk prediction. There is, therefore, a need to further identify the *types of data* that provide the greatest predictive accuracy, which types of assessments to prioritize, and in what *context* (e.g. specialized vs primary health care settings) multimodal prediction approaches are feasible and useful in predicting outcomes for individual patients. These issues will be addressed in the work of the current network.

5.3.4 Rationale for PRESCIENT assessment domains and measures

All of the assessment domains and measures to be used in PRESCIENT were decided through an extensive process of team discussion involving representatives from NIMH, PRESCIENT, ProNET, the DPACC, and AMP SCZ partners. This discussion led to a consensus harmonised assessment battery, i.e., a common battery of assessment domains and measures to be used across both recruitment networks (PRESCIENT and ProNET), allowing data to be pooled across both samples. A 2-month time point was chosen for the repeat biomarker assessments because: 1) the trajectory of change from baseline to 2 months has been found to be most useful for predictive modelling in existing data and 2) this time period can be used to inform the design of future clinical trials.

Clinical measures: Key considerations in the choice of clinical measures was to capture variables that have been found to be relevant to CHR outcomes, to capture the broad range of transdiagnostic symptomology present in this clinical population, and to minimise participant and assessor burden. As per previous studies, these measures will be integrated into a seamless clinical interview schedule.

Digital momentary assessments: Digital momentary assessments provide an ideal way of collecting data for digital phenotyping that can be used in dynamic prediction approaches. The most widely used and validated approaches for collecting these types of data are: i) intensive longitudinal EMA, the repeated (daily) sampling of a participant’s experiences and behaviours in its natural environment over an extended period of time using a smartphone app and ii) passive sensing in the form of monitoring gross motor activity (wearable accelerometer) and movement patterns (phone-based GPS data). Both approaches will be used in the current study.

Neurocognition: The neurocognitive assessment domains that have been included in the current study are those that have been found to be most relevant in previous CHR prediction research. The criteria considered in designing the battery included: being relatively culturally unbiased, computerised automated scoring, automated quality control and databasing, deployable in resource limited settings, reliability and validity, being repeatable, time efficient, amenable to advanced psychometrics, sensitive to sex as a biological factor and age effects, offering targets for treatment, being open source/public domain, amenable to remote administration, and offering genomic biomarkers.

Neurophysiology: EEG-based event-related potential and event-related oscillation measures are relatively inexpensive to acquire and provide direct measurements of summated neurophysiological activity with millisecond temporal precision. The rationale for inclusion of the paradigms and measures is summarized in the table below^{60, 61, 66, 67}.

Measure	Abnormal in schizophrenia	Abnormal in CHR	Predicts conversion to psychosis	Predicts CHR remission	Moderate to Strong Test-Retest Reliability	Altered by NMDA blockers in pharm challenge studies	Analog in rodent models
MMN	++	+/-	++	-	+	+	+
RP	+/-	+	+	-	?	?	+
Auditory Target P3b	++	+	++	+	+	+	-
Auditory Novel P3a	+	+	-	+/-	+	+	+
Aud Alpha Desynch	+	+	+	-	?	?	?
Visual Target P3b	+	+	+	+/-	+	+	-
Visual Novel P3a	+	+	+	+/-	+	+	+
40 Hz ASSR ITC	+	+	-/+	-	+	+	+

Resting State EEG Power Spectra, 1/f	+	+/-	+/-	+/-	+	+	+
--------------------------------------	---	-----	-----	-----	---	---	---

Biospecimens (blood and saliva samples): The biospecimens chosen are based on commonly reported and novel biomarkers, and those that have shown prospective associations with illness trajectories, both of psychosis^{68, 69} and mood and anxiety disorders⁷⁰. Alterations of the levels of several immune proteins and oxidative stress markers have been described in patients with psychotic and mood disorders, and such patterns may be indicative of trait or state characteristics⁷¹⁻⁷³. Serological studies suggest that some cases of schizophrenia and bipolar disorder may be associated with exposure to microbial infections⁷⁴. New ‘omic technologies now allow cost-effective screens of lipids, metabolites, proteins. Recent findings implicate the complement and coagulation pathway in predicting psychotic experiences and psychotic disorder⁷⁵⁻⁷⁷, and are therefore also included in the current battery. The genetic studies of the last decade have demonstrated that psychiatric disorders are highly polygenic and pleiotropic. Polygenic risk scores (PRS) can leverage the genetic information from the large genome-wide association studies (GWAS) to predict genetic risk in clinical samples. PRS are not accurate diagnostic tools, but can be considered as biomarkers that can become part of the predictive algorithm⁶⁵. Currently, the AUC associated with schizophrenia PRS is about 0.75, and those in the top 10% of a population distribution have an increased risk approximately equivalent to the risk of having an affected first degree relative. Blood samples will be used to isolated DNA for generation of PRS.

Evidence from two CHR cohorts suggests that the stress mediator cortisol is associated with conversion to psychosis^{68, 78, 79}. We have recently shown that a multisystem biomarker index reflecting immune activation, stress signalling and energy metabolism is associated with increased risk for persistent poor functioning in the CHR population⁸⁰. Given that both systemic inflammation and HPA-axis function are implicated not only in psychosis but also in mood disorders⁸¹, it is highly likely that such processes represent transdiagnostic risk mechanisms for emerging mental disorders, a target of investigation in the current study. Therefore, we will supplement the measurement of inflammatory response and oxidative stress via a saliva sample.

Speech and facial expression samples: Language production (e.g., indices of semantic coherence and syntactic complexity) has shown promise as a marker of psychosis risk^{82, 83}. A benefit of speech samples is that they are easily obtained and highly acceptable to patients. We are currently successfully collecting a large database of speech samples in CHR and first episode psychosis patients (supported through NIMH grant R01MH115332-01) and will extend this pool of data in the current assessment battery. Speech samples will be collected both in the context of an interview with a Research Assistant and in the course of daily life via a phone-based audio diary (see 8.5). In addition, disruption in facial expressivity⁸⁴ has been found to predict conversion to psychosis in CHR samples, and has therefore been incorporated into the current battery via video recordings during the open-ended speech collection interview.

Neuroimaging: Neuroimaging studies over the past twenty years have demonstrated significant associations between alterations in brain structure and connectivity and subsequent conversion to psychosis, with clear indications that these measures can improve individual prediction⁸⁵. There is also evidence that neuroimaging can provide predictive utility for outcomes other than conversion⁶⁴. The neuroimaging measures included in the current battery provide a comprehensive coverage of anatomy (brain volume, cortical thickness, etc.), microstructure (white matter), and both structural and functional connectivity. Measures derived from these acquisitions have been implicated in previous studies as abnormal in CHR populations and show dynamic changes between CHR and later stages of psychosis. The selection of measures and their particular parameters is optimized for the current state of the art analyses. Tier 1 is also expected to be relevant for analysis development over the next 5 years.

5.4. Study Aims

1. CHR Network Consolidation: Use the Australian Early Psychosis Collaborative Consortium (AEPCC) national platform to consolidate a network of CHR recruitment centres organised according to a 'hub and spoke' model, with Orygen functioning as the central hub with one Australian and nine non-Australian clinics as spokes. The network will: recruit a large sample of CHR patients (n=937) and a healthy control (n=250) sample; implement repeated multimodal assessments; map trajectories and outcomes over a 2 year period (conversion to psychotic disorder, persistent and incident non-psychotic disorders, non-remission of CHR status, persistent negative symptoms, psychosocial functioning, full recovery). This network of CHR recruitment centres will provide the clinical research infrastructure for future treatment trials in this clinical population informed by findings from the current program of work.

2. Prediction: In collaboration with the NIMH Steering Committee and the DPACC, the PRESCIENT dataset will be used to:

2a. Test the external validity of existing and forthcoming prediction models in the field (e.g., NAPLS, EU-GEI, PRONIA, PSYSCAN).

2b. Implement the model with strongest performance as an online risk calculator.

2c. Use the full AMP SCZ dataset to develop new, more refined prediction models and risk calculators drawing on recent theoretical and methodological advances (e.g., dynamic prediction, probabilistic multimodal modelling) and a range of biomarkers. These tools will guide stratification of patients in future clinical trials and may have clinical utility in decision making about stepping interventions up/down as risk is assessed over time (clinical trajectory, treatment response) and in response to incoming biomarker information, as well as guide stratification of patients in future clinical trials.

3. Validation: Internally and externally validate the prediction models generated in the AMP SCZ dataset. This will test the robustness, replicability and generalisability of the models' performance.

The purpose of recruiting a sample of healthy control participants is primarily to model site effects of biomarker measurement, particularly for neuroimaging data. However, this cohort also serves the purpose of: providing benchmark ‘normal’ levels on the various measures included in the schedule of assessments; modelling age effects; and assessing the stability of the biomarkers in healthy individuals.

5.5. Study Endpoints and Outcome Measures

Participants will be followed up at regular intervals over a 24-month period (see assessment schedule in 8.1). The primary outcome timepoint of interest is the 24-month follow point. Outcomes of interest are listed below:

Conversion to psychotic disorder. This is operationalised, as:

(A) At least one full threshold positive psychotic symptom as operationalised using the PSYCHS for one week or longer occurring (i) for more than an hour a day, 3-6 days per week OR (ii) daily for less than one hour

OR

(B) At least one full threshold positive psychotic symptom with the above frequency but lasting less than one week in the context of newly prescribed or newly increased antipsychotic medication

OR

(C) At least one full threshold positive psychotic symptom that is immediately dangerous – as assessed by the treating psychiatrist.

The projected number of converted cases across AMP SCZ is 300 (15% conversion rate)⁷.

*Remission of CHR status*⁷. The definition of remission from CHR status has previously been published⁸⁷ and is currently being used in our ongoing intervention trial²⁸. It is modelled on the schizophrenia course definitions presented by the Remission in Schizophrenia Working Group (RSWG)⁸⁸ and was agreed upon using a consensus process amongst CHR clinical and research experts. It requires no longer having attenuated psychotic symptoms in the CHR range, as assessed using the PSYCHS. For the Trait and State Risk Factor and Brief Limited Intermittent Psychotic Symptoms (BLIPS) groups, remission is defined as having achieved good functioning and no longer meeting criteria for schizotypal personality disorder (if present at baseline) and not having had onset of attenuated psychotic symptoms in the CHR range.

*Recovery from CHR status*⁷. Remission maintained for at least six months.

*Relapse of CHR status*⁷. Presence of CHR status after recovery (i.e., meeting PSYCHS severity, frequency and duration criteria for CHR status after recovery has been achieved).

Persistent non-psychotic disorders. A non-psychotic disorder which is present both at study entry and at outcome time point and from which full remission has not been achieved over

the interim. This will be determined using the Structured Clinical Interview for DSM-5 (SCID-5).

Incident non-psychotic disorders. A non-psychotic disorder present over the follow up period but not present at study entry. This will be determined using the SCID-5.

Persistent negative symptoms (PNS). As per our previous research⁸⁹, and consistent with the definition of Buchanan⁹⁰, PNS are defined as the presence of at least one Negative Symptoms Inventory (NSI) global subscale score ≥ 3 at baseline and at follow up, a combined total score of 6 or less on the Brief Psychiatric Rating Scale (BPRS) subscales of depression, guilt and suicidality (corresponding to an average of “very mild” or less on each item), and a combined total score of 16 or less on the BPRS psychotic subscales of conceptual disorganisation, hallucinations, suspiciousness and unusual thought content (corresponding to an average of “moderate” or less on each item).

Psychosocial functioning. SOFAS score at outcome time points.

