5.5.1. Primary outcome

The primary outcome of interest is conversion to psychotic disorder by 24 month follow up (definition in 5.4).

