7.2. Sample Size and Power

The size of the CHR sample is primarily determined by the aim of developing a prediction model for conversion to psychosis by 24 months (the primary outcome of interest). This will be achieved by combining data from the PRESCIENT and ProNET networks (i.e., the AMP SCZ dataset as whole), given that the protocols and schedule of assessments have been harmonised across the two networks. The projected CHR sample size for PRESCIENT is 937 and for ProNET 1,040 (combined n of 1,977). There is no uniform method for determining an adequate sample size for developing a prediction model⁹². In this sample size calculation, the method recently described by Riley et al⁹³ was used. Minimum sample size calculations required for various scenarios are provided in table 1. below. Specifically, the sample sizes were derived for the scenarios of having low, medium or high prediction performance and also for the number of parameters in the model being 10, 20, 30, 40 or 50. Conversion to psychosis is a time-to-event outcome and therefore a survival model such as Cox regression is appropriate. The table below shows the sample sizes for the survival outcome, assuming a conversion rate of 15% over 2 years (number of events=300).

Table 1. Minimum sample sizes for survival outcome.

		Number of parameters in model				
		10	20	30	40	50
Predictive performance	low	422	843	1265	1686	2108
	medium	398	796	1193	1591	1989
	high	366	732	1098	1464	1830

It is undesirable to have the number of parameters above 30 as this would result in a prediction model that is overly cumbersome in real-world settings. As indicated in the table, the minimum sample size for a model with 30 parameters is estimated to be between 1100 and 1300. However, as in all medical research, larger sample sizes lead to more robust models and it would therefore be desirable to achieve a sample size larger than this minimum recommendation. Therefore, we aim to assemble as large a sample as possible given the constraints of the length of the recruitment period and the number of recruitment sites. The sample size calculations presented in the table indicate that the overall AMP SCZ sample size of 1,977 is adequate for developing a prediction model with ~30 parameters that has high predictive performance, while still allowing a subset of the data to be 'held back' for external validation purposes (see section 14).

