TREATMENT AND HEALTH SERVICE UTILISATION	Psychosocial/ pharmacological treatment/service use		✓C	✓	✓C	✓			✓						✓C	✓	✓C	

Notes:

1. The Baseline visit needs to be conducted within 3 weeks of the screening visit. If not, the screening visit will need to be repeated. The study team will endeavour to schedule all other visits up to month 12 within +/- 1 week of their due date. For example, a Month 6 visit can occur up to 1 week prior to or after its due date. Month 18 and 24 will have a visit window of +/- 2 weeks. Assessments conducted outside these windows will be discussed with the local study team and the decision whether or not to utilize the data in analyses will be documented accordingly.
 2. Converted cases will be followed up as per the schedule of assessments. This will also be the case for participants who commence antipsychotic medication after study enrolment.
 3. Neurocognition tasks: Reading task in English speaking sites will be the WRAT5 Reading subtest; in non-English speaking countries the local version of the NART will be used. Apart from Premorbid and Current IQ, all other cognitive domains will be measured using the Web version of the Penn Computerised Neurocognitive Battery (PennCNB).
 4. The TBI will only be completed for participants where clinically indicated (i.e., participants who have had a traumatic brain injury, as reported by the participant or family or as determined from the participant's medical history).
 5. If conversion to psychosis is suspected based on the monthly BPRS assessment, then the PSYCHS and SCID will be conducted to check conversion status.
 6. Study participants will be contacted in between the formal assessments for the purposes of engagement and safety follow-up (see 8.12).

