8.3. Clinical Assessments

Informed by the recent advances in the field (see section 5.2), the study aims to collect multimodal data (clinical, biological, genetic, neurocognitive, neurophysiological, neuroimaging), baseline and repeat assessments over time ('macro' level monthly assessments) and 'micro-level' momentary (day-to-day) data collected through digital platforms (EMA and passive sensing). The 'macro' level repeat assessments are critical for both dynamic prediction of outcomes and also accurate characterization of clinical trajectories over time.

The battery of assessments are listed in 8.1 and described below. The selection of measures is informed by the Neurobiology in Youth Mental Health Partnership¹⁰¹, a national effort led by Orygen to standardize research assessments in order to create large datasets, guided by principles of feasibility, participant and clinical service burden, transdiagnostic relevance and translatability into clinical practice.

The following measures will be administered by RAs as part of an integrated clinical interview:

The **Positive Symptoms and Diagnostic Criteria for the CAARMS Harmonized with the SIPS (PSYCHS)** is a semi-structured interview which assesses symptoms associated with the prodromal phase of psychosis, and which is used to define the CHR criteria and onset of first-episode psychosis (FEP). The attenuated psychotic symptoms (positive symptoms) section of the PSYCHS will be assessed at all major assessment timepoints. This will be a rating of the worst period of each symptom either (1) over the last year (at Screener) or (2) since the participant's last research assessment.

The **Structured Clinical Interview for DSM-5 (SCID-5)** is a semi structured interview guide for determining DSM-5 diagnoses. The SCID-5-Research Version (RV)⁹⁷ will be used to assess DSM diagnostic criteria for Mood and Substance Use disorders and the SCID-5 Personality Disorders (PD)¹⁰² will be used to assess Schizotypal Personality disorder. If the participant converts to psychotic disorder, as determined using the PSYCHS, then the Psychotic Disorder section of the SCID-5-RV will be administered to determine type of DSM psychotic disorder. The language and diagnostic coverage

make the SCID-5 most appropriate for use with adults (age 18 and over); with slight modification to the wording of questions it may be used with adolescents.

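### As written, the primary outcome's frequency rule leaves out full-threshold symptoms present every day for an hour or more

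*Protocol*

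**What the plan says.** Section 5.5.1 states: "The primary outcome of interest is conversion to psychotic disorder by 24 month follow up". Section 5.5 gives the operational definition in three limbs.

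- Limb (A) asks for a full-threshold positive symptom, rated with the PSYCHS, that has lasted a week or more and fits one of two frequency patterns: "occurring (i) for more than an hour a day, 3-6 days per week OR (ii) daily for less than one hour".
- Limb (B): "At least one full threshold positive psychotic symptom with the above frequency but lasting less than one week", where antipsychotic medication has been newly started or increased.
- Limb (C): "At least one full threshold positive psychotic symptom that is immediately dangerous", in the treating psychiatrist's judgement.

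Section 7.2 fixes how the outcome is analysed: "Conversion to psychosis is a time-to-event outcome and therefore a survival model such as Cox regression is appropriate". Note 5 under the schedule in 8.1 says when status is checked between main visits: "If conversion to psychosis is suspected based on the monthly BPRS assessment, then the PSYCHS and SCID will be conducted to check conversion status". Section 8.3 makes the PSYCHS the instrument that defines both CHR status and the onset of first-episode psychosis. Neither note 5 nor 8.3 gives a frequency threshold, and the PSYCHS scoring rules are not reproduced.

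**The concern.** Both frequency patterns in limb (A) are closed at the top. Pattern (i) is capped at 6 days a week and pattern (ii) is capped below one hour, and neither is worded as a minimum. A full-threshold symptom present every day for an hour or more falls outside both. The rule therefore runs backwards at its upper end: a more frequent or longer-lasting symptom can fail where a lesser one passes.

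This is the only frequency rule the protocol gives for its primary outcome. That outcome supplies the event status and event date for the survival models, and it is the outcome on which the sample size rests. If the text were followed exactly, a participant with daily symptoms of an hour or more would not be counted under (A), unless an earlier week had met pattern (i) or (ii). If raters instead follow PSYCHS criteria that differ from this text, the protocol misstates its own primary outcome.

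**Working it through.** **The plan's own figure.** The only number tied to this definition is the projection of 300 conversions at 15% (sections 5.5 and 7.2). With the combined CHR sample of 937 + 1,040 = 1,977 from section 7.2, 0.15 × 1,977 = 296.55. That agrees with the rounded 300. The projection is not in dispute, and the point below does not depend on it.

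**The rule as logic.** Let d be days per week and h be hours per day. Limb (A) as written is met when

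(h > 1 and 3 ≤ d ≤ 6) or (d = 7 and h < 1).

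**Spot values.**

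- At 1.5, 4 or 12 hours a day, (A) is met for d = 3, 4, 5 and 6 and not met for d = 7.
- At d = 7, (A) is met at 0.5 hours and not met at 1, 1.5, 4 or 12 hours.
- At exactly 1 hour a day, (A) is not met for any d.

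**Full grid.** Seven day counts by three durations (under, exactly and over one hour) give 7 × 3 = 21 cells.

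| Reading of limb (A) | Qualifying cells | Count |
|---|---|---|
| As written | 3, 4, 5, 6 days over 1 h; 7 days under 1 h | 5 |
| Only (i) a minimum (3 or more days) | the same 5, plus 7 days over 1 h | 6 |
| Both patterns minimums | the same 5, plus 7 days at exactly 1 h and 7 days over 1 h | 7 |

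The written rule and the both-minimums reading differ by 7 − 5 = 2 cells, both daily. Exactly one hour on 3, 4, 5 or 6 days (4 cells) fails under all three readings. The cells describe the rule; they are not proportions of patients or events.

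**Whether the other limbs close the gap.** Limb (B) refers back to the frequency in (A), so a case excluded by that frequency is excluded from (B) too. Limb (C) has no frequency condition, but it counts such a case only if the symptom is immediately dangerous.

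**Whether another section supplies the rule.** Section 5.5.1 refers the reader to 5.4 for the definition, but 5.4 lists the study aims. The definition stands only in 5.5.

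**The case against.** The best defence is that the PSYCHS decides conversion, not this sentence. Limb (A) mentions the PSYCHS, section 8.3 treats conversion as determined by it, and the schedule and its note 5 use it to check status. The rest of limb (A) is also framed in minimums (at least one symptom, a week or longer), so the two patterns can be read as the mildest qualifying presentations, with more intense ones included. The literal reading makes a worse symptom disqualifying, which a trained rater is unlikely to accept.

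Much of this stands. The patterns were probably meant as minimums, nothing in the protocol shows that anyone will apply them literally, and no misclassified case is demonstrated. The exactly-one-hour case is a single boundary value and is secondary.

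The defence does not remove the defect. In limb (A) the reference to the PSYCHS attaches to the full-threshold symptom, after which duration and frequency are written out separately. Where section 5.5 wants the instrument to set frequency, as in its definition of relapse, it says so. In addition, sections 6.4 and 8.13 allow diagnostic status to come from medical records when a participant cannot be re-interviewed. In those cases no PSYCHS interview settles the question at that visit.

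**Conclusion.** The concern holds: limb (A) is wrong as written. Followed literally, it excludes full-threshold symptoms present daily for an hour or more, and limb (B) carries the same exclusion. Either the text governs and omits the most frequent presentation, or the instrument governs and the protocol misdescribes its primary outcome. Both call for correction.

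The size of the gap is known only in terms of the rule: 5 qualifying cells of 21 as written, against 7 if both patterns are minimums. The number of conversions affected cannot be derived, because the protocol gives no distribution of symptom frequency among converters, and no range is offered. Confidence is high for the literal gap and does not extend to any effect on event counts, event dates or model performance. The point should be fixed because it concerns the primary outcome, though the likely cause is a drafting slip.

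**What to change.** Reconcile the frequency wording of limb (A), and of (B) by reference, with the PSYCHS conversion criteria that raters actually apply. The text should state whether the two patterns are minimum frequencies. It should also say how daily symptoms of an hour or more, and symptoms of exactly one hour on 3 to 6 days, are classified. Which threshold is right is for the sponsor and the instrument's criteria to settle; none is proposed here.

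Use the reconciled rule wherever conversion status and date are derived, including status taken from medical records. The cost is one clarifying sentence in section 5.5, carried through to those derivations, with no added assessments.
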